### 1.2 Clinical Pharmacology Information

After SUBLOCADE injection in clinical studies, an initial buprenorphine peak was observed at approximately 24 hours post-dose. The initial peak was followed by a decline in plasma concentrations to a plateau throughout the monthly dosing interval, consistent with the slow release of buprenorphine from the SC depot. The apparent terminal plasma half-life of buprenorphine following SC injection of SUBLOCADE ranged between 43 to 60 days. Steady-state was achieved at 4 to 6 months following repeated monthly SC injections.

Buprenorphine is metabolized to its major metabolite, norbuprenorphine, primarily by cytochrome P450 3A4 and, to a lesser extent, by cytochrome P450 2C8. Norbuprenorphine can further undergo glucuronidation. Norbuprenorphine has been found to bind to mu-opioid receptors *in vitro*; however, norbuprenorphine is expected to have negligible contribution to brain mu-opioid receptor occupancy given its limited ability to cross the blood-brain barrier ([Ohtani 2007](#)) and has not been studied clinically for opioid-like activity. Norbuprenorphine steady-state plasma concentrations in humans after SC injection of SUBLOCADE were low compared with buprenorphine. The ratio of norbuprenorphine/buprenorphine areas under the plasma concentration-time curve (AUC) in a repeat-dose study (RB-US-12-0005) was 0.2 to 0.4, i.e., much lower than for transmucosal buprenorphine (ratio of 1.3-3.2 in the same study) due to the lack of first-pass effect.

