For the following descriptive analyses, the PK analysis set will be used. A graphical representation of buprenorphine and norbuprenorphine plasma/urine concentrations over time will be provided. Individual plasma/urine concentration-time data will be plotted using the time elapsed from the last SUBLOCADE dose. A solid line will be used to link concentrations from a same subject. Concentrations of buprenorphine and norbuprenorphine in urine (from quantitative UDS or free drug concentration assessments) will be presented with and without correction by creatinine concentration in urine (Appendix 4). The purpose of the correction by creatinine urine concentration is to correct for urinary dilution.

For plasma and urine (uncorrected) concentration-time plots, concentrations below the LLOQ will be imputed with the LLOQ value. Three symbols will be used for 1) quantifiable concentrations, 2) concentrations below the LLOQ and 3) quantifiable concentrations associated with the reported use of illicit buprenorphine at the visit or the use of prescribed buprenorphine within 3 weeks of the visit. For concentration-time plots representing buprenorphine or norbuprenorphine urine concentrations after correction with creatinine concentration in urine, concentrations below the LLOQ will not be imputed and will not be shown on the plots.

Norbuprenorphine-to-buprenorphine ratios will be calculated from quantifiable concentrations in plasma, quantifiable concentrations of free drug in urine, and quantifiable concentrations from quantitative UDS. Values will be reported in listings. Summary statistics (mean, SD, median, 5th and 95th percentiles, minimum, maximum) will be calculated by subgroups defined by the intake (yes/no) of prescribed or illicit buprenorphine. One subject may contribute to multiple observations (up to 3).

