Relationships between plasma and urine drug concentrations measured on the same day will also be explored by calculating urine-to-plasma ratios for quantifiable concentrations of buprenorphine or norbuprenorphine. Urine drug concentrations corrected by creatinine concentration or uncorrected will both be used to derive those urine-to-plasma concentration ratios. Values will be reported in listings. Summary statistics (mean, SD, median, 5th and 95th percentiles, minimum, maximum) will be calculated by subgroups defined by the intake (yes/no) of prescribed or illicit buprenorphine. One subject may contribute to multiple observations (up to 3).

Finally, plots will be constructed to assess the consistency of norbuprenorphine-to-buprenorphine ratios and of urine-to-plasma concentration ratios over time, using the time elapsed from the last SUBLOCADE dose. A solid line will be used to link data from a

same subject. Different symbols will be used by subgroups defined by the intake (yes/no) of prescribed or illicit buprenorphine.

Equations for correction of buprenorphine or norbuprenorphine urine concentrations or urine-to-plasma concentration ratios with creatinine concentration in urine are presented in Appendix 4.

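### Unless the norbuprenorphine LLOQ is several-fold below the buprenorphine LLOQ, computing plasma metabolite-to-parent ratios only from quantifiable pairs drops low ratios and biases the summaries upward near the limit

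*SAP*

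**What the plan says.** Protocol Section 3 lists the norbuprenorphine-to-buprenorphine ratio over time, in plasma and in urine, as an exploratory endpoint. SAP 13.1 sets the rule: "Norbuprenorphine-to-buprenorphine ratios will be calculated from quantifiable concentrations in plasma", and likewise for free drug in urine and for the quantitative urine drug screen. The ratios are summarised by mean, SD, median, 5th and 95th percentiles, minimum and maximum, split by buprenorphine intake (yes/no). SAP 13.1 adds that "plots will be constructed to assess the consistency of norbuprenorphine-to-buprenorphine ratios and of urine-to-plasma concentration ratios over time", against time since the last SUBLOCADE dose. Symbols on these plots differ only by intake.

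Concentration plots are treated differently. For plasma and uncorrected urine, "concentrations below the LLOQ will be imputed with the LLOQ value", with a separate symbol. In the population PK model, buprenorphine values below LLOQ are handled by a likelihood-based method (SAP 13.2.2). No rule covers a ratio in which one analyte is below LLOQ.

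On the expected level, Protocol 1.2 reports that the plasma AUC ratio in the repeat-dose study "was 0.2 to 0.4, i.e., much lower than for transmucosal buprenorphine (ratio of 1.3-3.2 in the same study"). Neither document states the plasma LLOQ of either analyte.

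**The concern.** At a ratio of 0.2 to 0.4, norbuprenorphine sits at one fifth to two fifths of buprenorphine. If the two LLOQs are similar, it becomes unquantifiable while buprenorphine is still measurable. Samples in that zone are not uninformative: each shows that the ratio lies below the norbuprenorphine LLOQ divided by the measured buprenorphine. The planned rule discards them and keeps samples from the same zone whose ratio is high enough to lift the metabolite over the limit.

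This is selection on the outcome, in one direction. It raises the mean, median and 5th percentile for samples near the limit. Because concentrations fall over the 12 to 36 month window, it can also tilt the across-subject picture upward with time. The direction matters because transmucosal buprenorphine gives a higher ratio ("ratio of 1.3-3.2 in the same study"), and undisclosed use is a confounder that this study captures largely by self-report.

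**Working it through.** There is no power or sample-size figure to reproduce, so the check starts with the SAP's PK inputs.

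**1. Inputs reproduce.** From SAP Table 1, k64 = 0.000510 per h, so ln 2 / 0.000510 = 1,359 h = 56.6 days. This lies inside the half-life in Protocol 1.2, which "ranged between 43 to 60 days". The interindividual variability formula 100 x sqrt(exp(variance) - 1) gives 30.2 for CL (variance 0.0871) and 73.5 for k64 (variance 0.432), as tabulated.

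**2. Truncation point.** Let B be buprenorphine, R the true ratio and N = R x B norbuprenorphine. Given quantifiable B, a ratio is computed only if R x B >= LLOQ_nor, that is R >= LLOQ_nor / B. With equal LLOQs (= L), a ratio of 0.4 is lost below B = L/0.4 = 2.5 L, and a ratio of 0.2 below B = L/0.2 = 5 L. B falls from 5 L to L in log2(5) = 2.32 half-lives: 2.32 x 43 = 100 days to 2.32 x 60 = 139 days.

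**3. Size by concentration, equal LLOQs.** Assume R is constant over time and log-normal with 0.2-0.4 as +/-1 SD: median sqrt(0.2 x 0.4) = 0.283, log-SD ln(2)/2 = 0.347, mean 0.283 x exp(0.347^2/2) = 0.30. B is log-uniform within each band.

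| B as multiple of LLOQ | Samples giving a ratio | Mean observed ratio (true 0.30) |
|---|---|---|
| 1-2 | 1% | 0.66 |
| 2-3 | 16% | 0.48 |
| 3-5 | 60% | 0.36 |
| 5-10 | 96% | 0.31 |
| 10-30 | 100% | 0.30 |

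If 0.2-0.4 is read as the central 90% instead, the means at 2-3x and 3-5x are 0.41 and 0.32 against a true 0.29.

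**4. Dependence on the LLOQs (same model).**

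| LLOQ_nor / LLOQ_bup | Band | Samples giving a ratio | Mean |
|---|---|---|---|
| 2 | 3-5x | 5.5% | 0.55 |
| 1/2 | 1-2x | 29% | 0.41 |
| 1/5 | 1-2x | 96% | 0.307 |

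**5. Size over time.** Buprenorphine was simulated from Table 1 (k36, k64, CL and F2 with their variances, covariates ignored), with visits uniform over 12-36 months and a constant true ratio of 0.28. Residual error was 19% on both analytes (the Table 1 value, assumed for norbuprenorphine). The CV of the ratio is not documented; 30% and 60% were tried. For 6 x 300 mg with equal LLOQs of 0.05 ng/mL (assumed), the observed geometric means were:

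| CV | 12-18 mo | 18-24 | 24-30 | 30-36 |
|---|---|---|---|---|
| 30% | 0.299 | 0.311 | 0.319 | 0.324 |
| 60% | 0.335 | 0.366 | 0.396 | 0.421 |

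Among samples with quantifiable buprenorphine, the share giving a ratio falls from 63% to 28% (CV 30%) or from 62% to 32% (CV 60%). With equal LLOQs of 0.02 to 0.1 ng/mL, the fitted change per 12 months is 1.05 to 1.29 fold with full Table 1 variability; the true value is 1.00. Halving the SD of k36 and k64 gives 1.19 to 1.77. With LLOQ_nor at one fifth (0.01 against 0.05), the means run from 0.279 to 0.277 (CV 30%) or 0.287 to 0.294 (CV 60%), essentially flat.

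**6. What one study would show.** With 60 subjects at Visit 1 and equal LLOQs of 0.05, about 8 ratios are expected. The fitted slope is positive in 58-63% of simulated trials, against 50% with no bias. Within subjects (half-life 43-60 days, Visit 1 buprenorphine 1-30x LLOQ, ratios at both Visits 1 and 3), the apparent change is 1.02 to 1.03 fold and 53% of lines rise.

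**7. Using the discarded samples.** Treating them as left-censored at LLOQ_nor / B brings the 12-month fold change to 0.96-1.00 (full variability) or 0.92-1.02 (halved).

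**The case against.** The strongest reply is that the effect depends on LLOQs that the documents do not give. That stands, and steps 4 and 5 show that at about one fifth there is almost nothing to correct. The analysis is also exploratory and untested, and the loss is partly visible elsewhere: plasma positives and negatives are counted per analyte, norbuprenorphine below LLOQ has its own symbol on the concentration plot, and all data are listed. But those counts are by visit rather than by time since dose, and none of this changes the ratio summaries.

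A reader might also infer more than the material supports:

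- *That late ratios are all unusually high.* This is true only for samples close to the limit. Table 1 spreads late concentrations so widely that most late survivors are subjects with high buprenorphine, hence the modest drift.
- *That Part B's purpose is defeated.* The Study Design text in the Protocol synopsis ties Part B to this ratio in urine, not plasma. A Part B line stops when the metabolite is lost; it hardly climbs.
- *That the drift would pass for transmucosal use.* For 6 x 300 mg at equal LLOQs of 0.05, the averages reach 0.32 to 0.42, and 0.50 for the other regimen at CV 60%. All are well short of 1.3. The 0.66 in step 3 applies to 1% of samples in one band.
- *That the SD is biased in a known direction.* In the model of step 3 it is 0.115 at 1-2x and 0.094 at 2-3x, against a true 0.108.

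**Conclusion.** The point holds in conditional form. The rule is explicit, it discards samples known to carry low ratios, and the ratio plot has no way to show them. Unless the norbuprenorphine LLOQ is several-fold lower than the buprenorphine LLOQ, the mean, median and 5th percentile of the plasma ratio are biased upward for samples near the limit. With equal LLOQs, the across-subject plot may drift upward by about 5-30% per 12 months with full Table 1 variability. A single study of 60 would show this only as a weak tendency, and within-subject Part B lines are little affected.

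The sizes rest on assumed LLOQs, an assumed spread of the ratio, an assumed norbuprenorphine residual error, and the use of an AUC ratio for single late samples. For urine, the documents do not show which analyte is lost first, so no direction can be claimed there.

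**What to change.** In SAP 13.1:

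1. When exactly one analyte is quantifiable, list and plot the ratio as a bound with an arrow symbol. Use an upper bound (norbuprenorphine LLOQ / measured buprenorphine) when norbuprenorphine is below LLOQ, and a lower bound (measured norbuprenorphine / buprenorphine LLOQ) when buprenorphine is. Apply this to plasma and to both urine assays. The lower bound is needed because Part B entry allows a positive norbuprenorphine result alone.
2. State both LLOQs, and report the number of ratios censored on each analyte beside the summary statistics.
3. Keep the planned all-quantifiable plasma summary. Beside it, give a sensitivity summary that treats the bounds as censored values, or one restricted to samples with buprenorphine at least 5 times the norbuprenorphine LLOQ. The restriction reduces the truncation without removing it: in the step 3 model, 16% of true ratios lie below 0.2.

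The cost is some SAP wording, arrow symbols and extra table columns, with no new data. The restricted summary would use fewer samples from an already small set. If the norbuprenorphine LLOQ proves low, the additions do no harm.

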#### **Study Design:**

This multicentre investigation will enrol subjects who participated in Study RB-US-13-0003 or both Studies RB-US-13-0003 and INDV-6000-301 and who received at least 2 SC injections of SUBLOCADE.

Part A will include all subjects who meet inclusion criteria and do not meet exclusion criteria. Data from subjects in Part A will be used to ensure a fully representative dataset for the distribution of plasma and urine data in the overall population within the time frame investigated (i.e., 12 to 36 months post the last SUBLOCADE injection). Buprenorphine plasma concentration data will be used to refine the existing population PK model for SUBLOCADE developed from Phase II/III study data, to provide accurate predictions for long-term plasma exposure to buprenorphine after discontinuation of SUBLOCADE treatment.

Part B will include subjects from Part A who meet continuation criteria as detailed below until a maximum of 30 subjects are enrolled. Data from subjects in Part B will inform the consistency of the PK profiles over time, the stability of urine-to-plasma ratios and norbuprenorphine-to-buprenorphine ratios in urine.

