### Part B

[figure not shown]
Results on the quantitative UDS performed at Visit 1 will determine enrolment in Part B: subjects who provide a quantifiable (i.e., positive) result for buprenorphine and/or norbuprenorphine and a non-quantifiable (i.e., negative) result for naloxone will meet continuation criteria to move on to Part B if Part B is still open to enrolment. Part B will consist of 2 visits, with 30 days ( $\pm 7$  days) between the visits.

At each visit, the same assessments as in Part A will be performed. In addition, the subject will answer a question regarding his or her illicit use of buprenorphine within the last 14 days.

Part B may meet enrolment and be considered closed to new subjects while Part A is still open to enrolment.

A schematic depicting the study design is in Figure 1.

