## **5 STUDY POPULATION SELECTION**

### **5.1 Number of Subjects**

Approximately 60 male or female subjects shall be enrolled in Part A.

A maximum of 30 Part A subjects will proceed into Part B (continuation part of the study).

Subjects who withdraw or are discontinued from the study will not be replaced.

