### **5.4 Part B Continuation Criterion**

Results on the quantitative UDS performed at Visit 1 will determine enrolment in Part B:

- Subjects who provide a quantifiable (i.e., positive) result for buprenorphine and/or norbuprenorphine and a non-quantifiable (i.e., negative) result for naloxone will continue into Part B of the study if Part B is still open to enrolment.
- Subjects who achieve negative results for both buprenorphine and norbuprenorphine quantitative UDS (irrespective of naloxone result) at Visit 1 will conclude their study participation, as will subjects who achieve a positive result for buprenorphine and/or norbuprenorphine and a positive result for naloxone on the quantitative UDS performed at Visit 1.

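### The SAP 13.1 ratio summaries pool up to three visits per subject, so no planned number separates within-subject from between-subject variation, which is what Part B's stability aim needs

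*SAP*

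**What the plan says.** The Study Design part of the Protocol synopsis gives Part B the task of informing, besides the consistency of PK profiles over time, "the stability of urine-to-plasma ratios and norbuprenorphine-to-buprenorphine ratios in urine". Entry to Part B is selective (Protocol 5.4): "Subjects who provide a quantifiable (i.e., positive) result for buprenorphine and/or norbuprenorphine and a non-quantifiable (i.e., negative) result for naloxone will continue into Part B", provided Part B is still open. Subjects negative for both analytes, or positive with naloxone present, stop after Visit 1.

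SAP 13.1 sets out the ratio analysis. Only measurable values count: "ratios will be calculated from quantifiable concentrations in plasma, quantifiable concentrations of free drug in urine, and quantifiable concentrations from quantitative UDS". The urine-to-plasma ratios follow the same rule. Mean, SD, median, 5th and 95th percentiles, minimum and maximum "will be calculated by subgroups defined by the intake (yes/no) of prescribed or illicit buprenorphine". For both kinds of ratio the section adds "One subject may contribute to multiple observations (up to 3"). It gives no split by visit or by study part, no one-value-per-subject summary and no within-subject statistic.

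The section also plans listings of every ratio, and plots of the ratios against time since the last dose, with each subject's points joined by a line and intake shown by symbol. Those plots are the stated means of judging consistency, in SAP 13.1 and in Protocol 14.5.

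Earlier in the same section, positive and negative results for the UDS, free drug in urine and plasma are tabulated for Part A at Visit 1 and for Part B across Visits 1, 2 and 3.

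**The concern.** The tables treat each subject-visit as a separate value, which has two consequences.

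First, a Part B subject can count three times and a Part-A-only subject once. If the two groups differ, the mean, median and percentiles lean towards Part B, and a reader may take them for a description of subjects.

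Second, a pooled SD adds visit-to-visit change within a subject to differences between subjects. Part B brings the same people back at roughly 30-day intervals to learn how much their ratios change, and the pooled SD cannot show that. The visit layout used for positivity is missing from the tables closest to Part B's purpose.

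At stake is whether the report can put a figure on ratio stability or must describe it from plots alone.

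**Working it through.** **Inputs from the documents.** Part A: "Approximately 60 male or female subjects shall be enrolled in Part A" (Protocol 5.1), one visit each. Part B: at most 30 of them (Protocol 5.1), with two further visits (Protocol 4.1).

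**Assumptions.** The documents give neither the within-subject correlation (ICC) of the ratios nor the number of Part-A-only subjects with a quantifiable ratio. I use ICC 0.1 to 1.0 and 0 to 30 such subjects. Every Part B subject is taken to give three ratios, which is the upper limit.

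**1. The plan's own figure.** 1 Part A visit + 2 Part B visits = 3 observations. This agrees with SAP 13.1.

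**2. Weighting.** With b Part B subjects and m Part-A-only contributors, Part B's share of values is 3b/(3b + m) and its share of subjects is b/(b + m). For b = 30:

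- m = 30: 90/120 = 75% of values, 30/60 = 50% of subjects; gap 25 points.
- m = 10: 90/100 = 90% against 30/40 = 75%; gap 15 points.
- m = 0: 100% against 100%; no gap.

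Fewer Part-A-only contributors raise Part B's share of values but shrink the over-weighting.

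**3. Effect on the mean.** If Part B differs from the others by d, the pooled mean moves by d × (share of values − share of subjects). For d = 1 SD that is 0.25 SD at m = 30 and 0.15 SD at m = 10. For d = 0 it is zero.

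**4. Effect on the percentiles.** A simulation (4,000 runs, normal values, SD 1 in each group, ICC 0.7, d = 1, 30 + 30 subjects) compared pooled values with one value per subject. The 5th and 95th percentiles moved from −1.26 and 2.26 to −1.02 and 2.47, and the SD from 1.12 to 1.08.

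**5. Effect on the SD when the groups share one distribution.** Expected pooled variance = s_w² + s_b² × k, where k = (N − Σn_i²/N)/(N − 1).

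- 30 + 30: N = 120, Σn_i² = 30 × 9 + 30 = 300, k = (120 − 2.5)/119 = 0.9874. At ICC 1 the SD is √0.9874 = 0.994, or 0.6% low.
- 30 + 0: N = 90, Σn_i² = 270, k = (90 − 3)/89 = 0.9775. At ICC 1 the SD is 0.989, or 1.1% low.

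If only 10 subjects enter Part B and nobody else contributes, k = 0.9310 and the SD is at most 3.5% low.

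**6. What the pooled SD says about stability.** Set the total SD to 1, so s_w = √(1 − ICC) and the pooled SD = √(1 − ICC + ICC × k), with k = 0.9874:

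| ICC | Within-subject SD | Pooled SD |
|---|---|---|
| 0.1 | 0.95 | 0.999 |
| 0.5 | 0.71 | 0.997 |
| 0.9 | 0.32 | 0.994 |

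The within-subject SD falls by a factor of three, while the pooled SD changes by about half a percent.

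**The case against.** The strongest reply is that the pooled table was never given the stability task. Protocol 14.5 and SAP 13.1 give it to plots with each subject's values joined, backed by full listings. The ratios are exploratory, the pooling is disclosed, and the plan is descriptive throughout: Protocol 14.1 rules out p-values and confidence intervals, and SAP 6.2 says no tests are performed. All of this stands, and it keeps the point small. It does not supply a number for visit-to-visit change.

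A reader might go further in several ways that the documents do not support:

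- **That Part B's stability aim is unaddressed.** The linked plots address it; only a numerical summary is missing.
- **That pooling distorts the SD.** With 30 Part B subjects the effect is about 1% or less unless the groups differ systematically.
- **That the over-weighting is worse in practice because urine-negative subjects drop out.** Step 2 shows the reverse.
- **That the reduced effective sample size matters.** No planned interval or test uses it.
- **That the tail percentiles will be used to tell depot release from recent use, and rest on one or two people.** No such use is stated. One value per subject would not help either, since 5% of 30 subjects is 1.5 people.
- **That a subject appearing in both intake groups is an error.** Intake can change between visits, so classing each observation by its own visit is sound. The SAP should say that this is what it does.

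One value per subject taken at Visit 1 would also be a poor remedy. SAP 13.1 treats Visit 1 as free of recent use, and the illicit-use question is asked only at Visits 2 and 3 (Protocol Appendix 1), so the intake-yes group would be empty.

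**Conclusion.** The point holds as a minor one. The ratio summaries pool up to three visits per subject and give Part B subjects up to three times the weight of others. With 30 Part B subjects the excess runs from 25 percentage points down to none, depending on how many Part-A-only subjects have a quantifiable ratio. That number may differ from ratio to ratio.

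Whether the weighting moves the mean or percentiles depends on a difference between the groups that the documents do not establish. Protocol 1.2 reports norbuprenorphine/buprenorphine AUC ratios of 0.2 to 0.4 for SUBLOCADE and 1.3 to 3.2 for transmucosal product. A difference would therefore be plausible if naloxone-positive Part-A-only subjects had used transmucosal product, but that link is an inference. The 1 SD difference above is illustrative.

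The firmer conclusion does not depend on such a difference: a pooled SD cannot separate within-subject from between-subject variation. As planned, stability will be judged from plots and listings, with no figure to report. The analysis is exploratory and nothing inferential rests on it.

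**What to change.** Amend SAP 13.1 as follows:

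- Summarise each ratio by visit, for Part A at Visit 1 and for Part B at Visits 1, 2 and 3, matching the layout of the positivity tables.
- State that intake is classified per visit. The rule already used for the concentration-time plot symbols would serve: reported illicit use at the visit, or prescribed use within 3 weeks of it.
- For Part B subjects, report within-subject and between-subject CVs from the log ratio, using visits without reported intake. The variance components can be converted with √(exp(variance) − 1), the formula under SAP Table 1. The within-subject CV includes any trend between visits, so read it beside the by-visit tables.
- Keep the plots, the listings and the pooled intake-yes/no summary, labelling the last as counts of subject-visits.

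All of this is descriptive, so it needs no tests or confidence intervals and respects Protocol 14.1. It uses data already planned for collection. The cost is a short SAP change and a few extra tables.
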